# LIST OF ABBREVIATIONS AND RELEVANT DEFINITIONS

ABR	ABR form, General Assessment and Registration form, is the application form that is required for submission to the accredited Ethics Committee (In Dutch, ABR = Algemene Beoordeling en Registratie) Adverse Event
AR ASRM BD CCMO	Adverse Reaction Altman Self Rating Mania Scale Bipolar Disorder Central Committee on Research Involving Human Subjects; in Dutch: Centrale
CHIME DSMB	Commissie Mensgebonden Onderzoek Comprehensive Inventory of Mindfulness Experience Data Safety Monitoring Board
	Functioning Assessment Short Test
MBCT	Mindfulness Based Cognitive Therapy
METC	Medical research ethics committee (MREC); in Dutch: medisch ethische toetsing commissie (METC)
MHC-SF	Mental Health Continuum – short form
QIDS-SR	Quick Inventory of Depressive Symptomatology – Self report
RPA-NL	Responses to Positive Affect- Dutch version
RRS	Ruminative Response Scale
(S)AE	(Serious) Adverse Event
SCS-SF	Self-Compasstion Scale – short form
SCID-I	Structured Clinical Interview for DSM-IV-TR Axis I Disorders
Sponsor	The sponsor is the party that commissions the organisation or performance of the research, for example a pharmaceutical
	company, academic hospital, scientific organisation or investigator. A party that provides funding for a study but does not commission it is not regarded as the sponsor, but referred to as a subsidising party.
TAU	Treatment as usual
TiC-P	Trimbos/iMTA questionnaire for costs associated with psychiatric illness
STAI	State/Trait Anxiety Inventory
Wbp	Personal Data Protection Act (in Dutch: Wet Bescherming Persoonsgevens)
WMO	Medical Research Involving Human Subjects Act (in Dutch: Wet Medisch- wetenschappelijk Onderzoek met Mensen
VMDC	Young Mania Bating Scale

YMRS Young Mania Rating Scale

#### SUMMARY

**Rationale:** Persistent and residual depressive symptoms in bipolar disorder (BD) are common and have been associated with negative effects on the course of BD. However, limited data are available on how to reduce these depressive symptoms, or how to improve outcomes for patients who do not benefit sufficiently from available treatments. Mindfulness-Based Cognitive Therapy (MBCT) is an innovative intervention that already has been shown effective in reducing depressive symptoms in unipolar recurrent depression. Therefore, it is hypothesized that, compared to usual care, MBCT will reduce depressive symptoms in BD patients.

**Objective**: Outcomes of MBCT for BD patients are examined on a symptomatic level (e.g. depression, (hypo)mania, anxiety, risk of relapse/recurrence) and in terms of functioning and mental health/wellbeing, including possible working mechanisms such as improvements of mindfulness and selfcompassion skills.

**Study design:** A randomized, multicenter, evaluator-blinded, prospective clinical trial with assessments at baseline, and 3, 6, 9, 12 and 15 months follow-up.

**Study population:** Adult BD type I or BD type II patients (N = 160) who suffered from at least two lifetime depressive episodes (either current or in (partial) remission), and having suffered from at least one affective episode within the year prior to baseline, without (hypo)manic symptoms within the last 3 months.

**Intervention:** Patients will be randomly assigned to one of two groups: (1) Treatments as usual (TAU): Patients continue to receive usual care, typically consisting of pharmacotherapy, psycho-education and self-management interventions. (2) TAU + MBCT: Patients will be invited to participate in a MBCT-program in addition to their usual care.

**Main study parameters/endpoints:** Primary outcome is the severity of depressive symptoms at 3 months follow-up (T1), assessed with the Inventory of Depressive Symptomatology – Clinician administered (IDS-C; Akkerhuis, 1997).

Nature and extent of the burden and risks associated with participation, benefit and group relatedness: The burden associated with participation in MBCT is relatively high: consisting of 8 weekly group sessions of 2,5 hours and one silent day (6 hours), and home practice of about 45 minutes a day. Participation includes 6 research assessments consisting of interviews and questionnaires about psychological symptoms, functioning, and quality of life. Before and after the intervention the assessment will include computer tasks to assess cognitive control. Although the effort requested from patients is high, we expect that practicing mindfulness will be associated with enduring changes in patients' coping strategies in daily life, and as a result, can increase participants' autonomy and self-efficacy. The risks associated with participation are expected to be low. Although the increased awareness of difficult emotions may be confronting or overwhelming for some, this is a major topic that will be discussed during MBCT. If participants show a clear increase in symptoms, this will be discussed to respect their boundaries (both physical and psychological) and are always free to suspend or adapt the practice as needed.

#### 1. INTRODUCTION AND RATIONALE

Bipolar Disorder (BD) is characterized by its severe and chronic course, with patients suffering from recurrent depressive, (hypo)manic, and/or mixed episodes, being symptomatic about half of the time (Judd et al., 2002). According to the World Health Organization (2008), BD belongs amongst the leading causes of years lost due to disability. BD patients typically experience debilitating psychological stressors, such as social rejection, internalized stigma, and subjective distress (Davis & Kurzban, 2012), and is therefore associated with tremendous economic, social, and occupational burden (Dilsaver, 2011; McCrone, Dhanasiri, Patel, Knapp, & Lawton-Smith, 2008; Pini et al., 2005). In the Netherlands. BD affects approximately 1.2% of men and 1.4% of women (De Graaf, Ten Have, & van Dorsselaer, 2010). Although hospital admissions are more common during manic episodes, it has been shown that depressive symptoms substantially predominate over manic symptoms, and that illness-related disability is more strongly influenced by depressive episodes (Judd & Akiskal, 2003; Judd et al., 2002). It has been estimated that approximately 33 – 50% of BD patients attempt suicide at least once in their lifetime, whilst 15 - 20% die due to suicide (Gonda et al., 2012). Since the middle of the last century, pharmacological interventions have been the first-line treatment for BD (Vieta & Colom, 2004). However, it has become evident that pharmacological interventions alone are insufficient, since 60% of patients relapse within two years (Miklowitz et al., 2009; Oud et al., 2016). Therefore, augmentation of psychological interventions is required in order to improve symptoms and reduce relapse rates (Oud et al., 2016; Vieta & Colom, 2004). Adjunct psychosocial interventions appear to improve outcomes as patients learn to adopt behavioural strategies to manage their mood instability. However, in spite of these interventions, persistent or residual depressive symptoms remain in more than 40% of patients (Samalin, de Chazeron, Vieta, Bellivier, & Llorca, 2016). These symptoms are strongly associated with impairments in interpersonal and occupational functioning (Dilsaver, 2011; Samalin et al., 2017), and affect the course of BD and quality of life negatively (Gutiérrez-Rojas et al., 2008). Furthermore, these adjunct psychological interventions seem to become less effective in those who suffered more than twelve previous episodes (Scott et al., 2006). Limited data are available on how to optimize treatment of persistent or residual depressive symptoms in BD, or how to improve outcomes for patients who do not benefit sufficiently from available treatments. Furthermore, there is a need for interventions that not only target symptom reduction but also help patients to cope with their illness from a wider perspective, i.e. in terms of their personal values, goals, and social roles (Farkas, 2007).

Mindfulness-Based Cognitive Therapy (MBCT), an innovative psychological intervention, has been shown effective in reducing depressive symptoms in unipolar recurrent depression (Kuyken et al., 2016; van Aalderen et al., 2012), and appears to be promising for coping with severe mental illness (Davis & Kurzban, 2012). Little is known about the effectiveness of MBCT for BD, with only a number of pilot studies showing reductions in depressive symptoms (Miklowitz et al., 2009; Williams et al., 2008), and one RCT showing a reduction of anxiety symptoms but not of depressive symptoms (Perich, Manicavasagar, Mitchell, Ball, & Hadzi-Pavlovic, 2013). The study of Perich et al. (2013), however, showed high drop-out rates, which may have compromised the power to detect changes in depressive symptoms, especially given the fact that this was an euthymic group at baseline. Thus, there is a lack of sufficiently powered RCTs examining the effect of MBCT on BD patients. In addition, most studies have included remitted BD patients only, which may have limited the possible range of symptom reduction and the clinical representativeness of the studies. The proposed study will be the first RCT of MBCT for BD in the Netherlands, providing high-level evidence about the effectiveness of MBCT versus TAU for patients with BD. It will be offered in a multi-centre setting and using several outcome measures, including cost-effectiveness. If (cost-)effective, MBCT might widen the array of psychosocial interventions for patients with BD.

Growing evidence conceptualizes BD as having difficulties in emotion regulation (Gruber, Eidelman, & Harvey, 2008; Gruber, Eidelman, Johnson, Smith, & Harvey, 2011). Rumination of both positive and negative affect has been associated with the onset and maintenance of BD (Johnson, 2005; Nolen-Hoeksema, 1991). Ruminative responses to negative affect appear to create a vicious cycle of ruminative thinking, decreased motivation and interest, and loss of positive mood, which intensifies symptoms of depression (Johnson, McKenzie, & McMurrich, 2008), whilst rumination of positive affect

is associated with goal-directed activity and decreased sleep, which intensifies symptoms of mood elevation (Gruber, 2011). According to Segal, Williams, and Teasdale (2002), training in mindfulness should decrease the tendency of depressed patients to enter a vicious cycle of negative ruminative thinking. Studies investigating reductions of negative rumination during MBCT are scarce (Michalak, Holz, & Teismann, 2010). In a sample of 55 treatment-resistant depressed patients, Eisendrath et al. (2008) found significant reductions of negative rumination following MBCT. The study of Deckersbach et al. (2012) found a significant decrease of negative rumination after MBCT in a sample of ten BD patients. Other studies found statistical trends towards reductions of negative ruminative thinking after MBCT in a sample of 19 patients with residual depressive symptoms (Kingston, Dooley, Bates, Lawlor, & Malone, 2007), and 95 BD patients (Perich et al., 2013). To our knowledge, no studies to date have investigated the effect of MBCT on ruminative responses to positive affect in BD patients. The present study will be the first to examine differences in ruminative responses to both positive and negative affect following MBCT in BD patients.

Furthermore, little is known about the potential moderators and working mechanisms of recovery in BD. One of the possible moderators of MBCT for patients with recurrent depression is a history of childhood traumatic events (CTEs; Williams et al 2014). CTEs also play a major role in BD. For example, CTEs are associated with higher risk of developing bipolar disorder and critically with a more severe clinical presentation over time (Aas et al., 2016). To find whether CTEs also have an influence on the effect of MBCT on BD, another goal of this study is to investigate whether the subgroup of patients with CTEs show a differential response to MBCT compared to subjects without CTEs. Moreover, CTEs contribute to the development of negative cognitive schemas, a finding that has mainly been described in patients with depression (Beck & Haigh, 2014; Gotlib & Joormann, 2010; Mathews & MacLeod, 2005). These schemas conceptualized on a cognitive level as a coalescence of different cognitive-affective biases (e.g. in attention and memory) leading to a biased view towards the self, the future and the environment, sustaining clinical symptoms in depression such as emotion dysregulation (Beck, 2008; Beck & Haigh, 2014). Research on cognitive bias in BD is limited and results are equivocal (Peckham, Johnson, & Gotlib, 2016). Findings include no attentional bias in euthymic BD patients (e.g. Peckham et al., 2016), but critically diminished attention towards positive words in mildly depressed BD patients (Jabben, Arts, van Os, & Krabbendam, 2010) and depressive mood-related negative recall bias in BD patients (Adams, Shapero, Pendergast, Alloy, & Abramson, 2014). It seems warranted to investigate whether MBCT results in changes in different forms (e.g. attentional memory) of these cognitive-affective biases in BD patients. If so, we will be able to advance our insight in the potential cognitive-affective working mechanisms of MBCT in BD.

In sum, the current study will combine measures of clinical and cost-effectiveness with cognitive measures addressing cognitive-affective bias and other psychological processes including rumination, mindfulness and self-compassion to assess the potential mechanisms of change in MBCT for bipolar disorder.

## 2. OBJECTIVES

Primary Objective:

• Is MBCT as an adjunctive treatment to TAU more effective in reducing depressive symptoms in patients with bipolar disorder, compared to TAU alone?

Secondary Objective(s):

- Is MBCT more effective than TAU in reducing levels of (hypo)manic and anxiety symptoms, the risk of relapse in depression or (hypo)mania, and ruminative brooding?
- Is MBCT equally effective in patients with < 12 mood episodes compared to patients with =/> 12 episodes?
- Is MBCT more effective than TAU in improving mindfulness, self-compassion, functioning, and mental health/well-being?
- From the viewpoint of the society, is adding MBCT to TAU preferable in terms of societal costs and QALYs, compared to TAU alone?

Our hypothesis is that participants allocated to MBCT will have fewer depressive, (hypo)manic, and anxiety symptoms and experience fewer (hypo)manic or depressive episodes than those allocated to TAU over the 15 months study period. In addition, we hypothesize that MBCT will be associated with improvement in several areas of functioning and well-being. Furthermore, we expect that positive outcomes will be (partially) mediated by a reduction of ruminative thinking, and improvement of mindfulness and self-compassion skills.

#### 3. STUDY DESIGN

A randomized, multicenter, prospective, evaluator-blinded clinical trial of MBCT added to treatment as usual (TAU) versus TAU alone. Assessments will be conducted at baseline and at 3, 6, 9, 12, and 15 months follow-up. At the end of the study period (15 months), the participants in the TAU group will be offered MBCT as well. Three external, specialized outpatients clinics for treatment of BD, will be participating in the present study. See Figure 1 for a prospective flow chart of the study.

Figure 1. Prospective flow chart of the study

#### 4. STUDY POPULATION

## 4.1 **Population (base)**

BD patients older than 18 years will be recruited from the specialized outpatient clinics of ProPersona, Dimence, and Altrecht, and through the Vereniging voor Manisch Depressieven en Betrokkenen (VMDB). The psychiatry department of the Canisius Wilhelmina Ziekenhuis (CWZ) will also support recruitment by referring potential participants to the Raboudumc.

#### 4.2 Inclusion criteria

In order to be eligible to participate in this study, participants have to meet all of the following criteria:

- Confirmed diagnosis of bipolar I or II disorder.
- Having suffered at least two lifetime depressive episodes, either current or in (partial) remission at baseline (according to SCID-I assessment).
- Having suffered at least one affective episode (depressed or (hypo)manic) within the year prior to baseline.
- Young Mania Rating Scale score < 8.

## 4.3 Exclusion criteria

A potential participant who meets any of the following criteria will be excluded from participation in this study:

- A manic episode within three months before the start of the trial.
- Lifetime diagnosis of schizophrenia or schizoaffective disorder, current substance abuse disorder, organic brain syndrome, antisocial or borderline personality disorder.
- Risk of suicide or aggression.
- The presence of a concurrent significant medical condition impeding the ability to participate.

## 4.4 Sample size calculation

Sample size calculation is based on the estimated change in depressive symptoms form pre- to posttreatment. As we aim to include patients with all levels of depressive symptoms, we based our calculation on a previous study conducted at the Radboudumc Centre for Mindfulness (van Aalderen et al., 2012). In this study, levels of depression as assessed with the Inventory of depressive symptomatology – self-rated (IDS-SR) decreased in the MBCT+TAU group (n = 102) from 14.9 ( $\pm$  9.2) to 10.3 ( $\pm$  7.8) whereas the TAU group (n = 103) showed no change in depression levels (pretreatment: M = 16.2 ( $\pm$  9.4) and posttreatment: M = 16.2 ( $\pm$  9.8). This corresponded to an effect size of 0.5 for reduction of depressive symptoms in patients with recurrent (unipolar) depression (remitted n = 124, currently depressed n = 58). Based on a two-sided test with an alpha of 0.05 and a power of 80%, with an estimated effect size of 0.5, including a design factor of 1 – r2 (0.75), and taking account of a conservative estimate of 40% loss to follow-up, we intend to recruit N = 160 patients (80 per group).

We anticipate that about 25% of the population will have to be excluded due to (hypo)manic symptoms (when exceeding the maximum on the Young Mania Rating Scale) or other exclusion criteria. We further expect about 25% of the eligible patients to be interested in the study.

Approximately 690 BD patients are treated in ProPersona, with 518 (75%) meeting the inclusion criteria, of whom 130 (25%) would probably be interested to participate. The intended number of participants (n = 60) falls comfortably within this estimate. The number of BD patients treated in Dimence is about 900, with 675 (75%) meeting the inclusion criteria, of whom 169 (25%) would probably be interested to participate. Again, the intended number of participants (n = 50) falls well within this estimate. Approximately 650 BD patient are treated in Altrecht, with 100-150 new patients per year. About 487 (75%) of BD patients would be meeting the inclusion criteria, of whom 122 (25%) would probably be interested. The intended number of participants (n = 50) therefore seems feasible. Moreover, we will recruit patients through the patient association Vereniging voor Manisch Depressieven en Betrokkenen (VMDB) and the psychiatry department of the Canisius Wilhelmina

Ziekenhuis (CWZ). Patients whose attending physician is not affiliated with one of the participating centres will be asked permission to inform their attending physician about the patient's participation in the study.

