## 5. TREATMENT OF SUBJECTS

## 5.1 Investigational treatment

## Mindfulness Based Cognitive Therapy (MBCT) + TAU

This intervention will consist of usual care, with MBCT in adjunct. MBCT is a manualised group skillstraining program (Segal, Williams, & Teasdale, 2012) designed as a relapse prevention programme for patients with recurrent depression. The training consists of eight weekly sessions of 2.5 hours, plus one day of silent practice. In addition, participants are instructed to practice 45 minutes a day. The program includes both formal and informal meditation exercises. Cognitive techniques that are part of the program include psychoeducation, monitoring and scheduling of activities, identification of negative automatic thoughts and devising a relapse prevention plan. The MBCT intervention offered in the current study will be based on the 8-week MBCT course developed by Segal et al. (2012), but will be adapted to address the needs of BD patients. A few examples of these adaptations are as follows: psychoeducation about manic symptoms in addition to psychoeduction about depression; introducing the 3-minute breathing space earlier in the programme and more often during sessions, especially when strong emotions are present; repeatedly bringing the focus to self-care; and making use of the mindful movement (yoga) exercises more frequently. All group sessions will be conducted at the respective mental health sites, with each group comprising 8 - 12 participants.

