#### 6.1.1 Main study parameter/endpoint

The primary endpoint of the study is severity of depressive symptoms at 3 months follow-up (T1), assessed with the *Inventory of Depressive Symptomatology – Clinician administered* (IDS-C; Akkerhuis, 1997). The IDS-C has good psychometric qualities (Rush, Gullion, Basco, Jarrett, & Trivedi, 1996; Trivedi et al., 2004) and will be administered by trained research assistants.

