## 6.2 Randomisation, blinding and treatment allocation

Randomisation will be performed within the datamanagement system Castor EDC. This will consist of stratified, variable block randomisation with the following stratification variables: Location (site); Gender; Depression (current versus remitted); BD type (I versus II); and number of previous episodes (<12 versus =/> 12). This system also allows for blinded (concealed) allocation such that research assistants on site can be kept blind to condition. MBCT teachers on site will be notified of the allocation to MBCT, allowing them to invite the patient to participate and coordinate further arrangements. As only assessors will be blind to treatment allocation due to the nature of the intervention, no indications for breaking the randomization code are pre-specified. In case of adverse reactions, patients are encouraged to discuss this with their MBCT teacher and responsible clinician.

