## 6.6 Follow-up of subjects withdrawn from treatment

Dropouts will be contacted by phone and asked to fill out the remaining questionnaires to supply the researchers with a post measurement and follow-up. Dropouts will be reminded that they are free to refuse.

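### The 80% power quoted for N = 160 omits the MBCT therapy-group effect that section 8 fits, and section 8.1 does not secure the baseline adjustment that the calculation relies on

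*Protocol*

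**What the plan says.** Section 4.4 uses a two-sided 5% test and 80% power, "with an estimated effect size of 0.5, including a design factor of 1 – r2 (0.75"), then "taking account of a conservative estimate of 40% loss to follow-up", and concludes "we intend to recruit N = 160 patients (80 per group"). It gives no ICC, number of therapy groups or allowance for clustering. The only design factor it names reduces N.

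Section 6.1.1 fixes the endpoint in time: "The primary endpoint of the study is severity of depressive symptoms at 3 months follow-up (T1"). Section 5.1 sets how MBCT is delivered: "All group sessions will be conducted at the respective mental health sites, with each group comprising 8 - 12 participants".

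Section 8 nests MBCT patients within their therapy groups and adds a random effect for group. It treats the pre- and post-measurements together as the outcome, and adds covariates for those baseline parameters that turn out unequal between arms. Section 8.1 lists baseline among the repeated IDS-C measurements. It does not say that baseline IDS-C is a covariate, or that the arms share one baseline mean.

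**The concern.** The power in 4.4 belongs to a different model from the one in section 8, in two respects.

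First, outcomes of patients treated in the same MBCT group may be correlated. The analysis plan recognises this and the sample size does not. Any positive correlation raises the variance of the MBCT mean, and the test then rests partly on the number of groups rather than the number of patients.

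Second, multiplying by 1 – r² is justified only if the analysis conditions on baseline IDS-C or holds its mean equal across arms. A model with a separate baseline mean in each arm does not earn that gain in full, and sections 8 and 8.1 allow such a model.

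At stake is a higher chance of missing a true 0.5 SD effect than the stated 20%, part of which is avoidable. The treatment estimate itself is not biased.

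**Working it through.** **Reproducing N = 160.** Inputs from 4.4: d = 0.5 (SD = 1), two-sided alpha 0.05, factor 0.75 (so r = 0.5), loss 40%. A two-sample t-test with 64 per arm has 80.1% power. Then 64 × 0.75 = 48 completers per arm, and 48 / 0.6 = 80 randomised per arm. Power at 48 per arm with residual variance 0.75 is 79.9%, so nothing is left over.

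**Number of MBCT groups.** One site's target is given as "The intended number of participants (n = 60) falls comfortably within this estimate", and the other two are 50 each. Split 1:1, that is 30, 25 and 25 MBCT patients. With 8–12 per group, 25–31 patients fit only as 3 groups, 24 fit as 2 or 3, and 22–23 only as 2. The planned split therefore gives 9 groups. Exact splits are not assured, because allocation is by "stratified, variable block randomisation with the following stratification variables: Location (site") and four further two-level factors (3 × 2 × 2 × 2 × 2 = 48 strata). If one or both smaller sites run two groups, the total is 8 or 7. A split of 32/24/24 could give 10.

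**Power with the group effect.** Let n be the number analysed per arm, k the number of groups and m = n/k, with the ICC on the baseline-adjusted residual:

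- MBCT arm: V1 = 0.75 × (1 + (m – 1) × ICC) / n
- TAU arm: V2 = 0.75 / n
- Noncentrality = 0.5 / √(V1 + V2)
- df = 2n – 2 (residual), or (V1 + V2)² / (V1²/(k – 1) + V2²/(n – 1)) (Satterthwaite)

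Example with n = 48, k = 9, ICC = 0.05: m = 5.33, V1 = 0.01901, V2 = 0.01563, noncentrality 2.69. Power is 75.8% with df = 94 and 73.1% with Satterthwaite df = 23.8.

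The ICC values and the 20% loss are assumptions; the documents give neither.

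| T1 loss | Groups | Residual df, ICC 0.02/0.05/0.10 | Satterthwaite df, ICC 0.02/0.05/0.10 |
|---|---|---|---|
| 40% (n = 48) | 10 | 78.5/76.3/72.8% | 76.5/74.1/70.2% |
| 40% (n = 48) | 9 | 78.3/75.8/71.8% | 76.0/73.1/68.7% |
| 40% (n = 48) | 8 | 78.0/75.2/70.7% | 75.2/72.0/66.8% |
| 40% (n = 48) | 7 | 77.7/74.4/69.2% | 74.3/70.4/64.4% |
| 20% (n = 64) | 9 | 88.2/85.5/81.0% | 86.2/83.0/77.6% |

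With 9 groups and 40% loss, Satterthwaite df gives 77.9% even at ICC 0, so about 2 points come from the df method alone. With 9 groups, N = 160 keeps 80% power up to a T1 loss of 37/33/23% (residual df) or 33/27/13% (Satterthwaite).

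A simulation of 40,000 runs (9 groups, Welch–Satterthwaite test on group means) gave 75.6/72.7/68.2% at n = 48 and 86.1/82.5/77.0% at n = 64, with type I error 4.8–5.2%.

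**Free baseline means.** If all 80 per arm supply baseline and n supply T1, a separate baseline mean in each arm adds 0.25/80 to each arm's variance. At 40% loss this is 0.75/48 + 0.25/80 = 0.01875 per arm, and 0.01875 × 48 = 0.90, so the effective factor is 0.90 rather than 0.75. Before clustering, power falls from 79.9% to 72.4%. With 9 groups and Satterthwaite df it is 68.5/66.1/62.3%, a loss of 7.5/7.0/6.4 points. At 20% loss it is 82.1% before clustering (7.9 points lower) and 77.9/74.9/70.0% with 9 groups and Satterthwaite df (8.3/8.1/7.6 points lower).

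**The case against.** N = 160 is not an arithmetic error, and the size of the shortfall depends on values outside the protocol.

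- **Loss at T1.** The 40% is called conservative and is not tied to T1, while follow-up runs to 15 months. Section 6.6 also plans to recover data: "Dropouts will be contacted by phone and asked to fill out the remaining questionnaires". At 20% loss only one of the six 9-group figures is below 80%. This stands, and it is why the result must be stated conditionally.
- **ICC.** At ICC 0.01, with 9 groups, 40% loss and residual df, power is 79.1%, which is under 1 point short. This also stands: the shortfall may be small.
- **Satterthwaite df.** This method is not in the protocol. True, which is why both sets of figures are given. The residual-df figures at 40% loss are below 80% too.
- **Unequal SDs.** The earlier trial cited in 4.4 had post-treatment SDs of 7.8 (MBCT) and 9.8 (TAU), so clustering would inflate the smaller variance. Using that ratio gives 77.2/75.1/71.6% with Satterthwaite df: better by one to three points, still below 80%.
- **Larger effect.** The earlier trial's means could support a larger adjusted effect. At 0.56 SD, power at 40% loss would be 84.7/82.3/78.2%. That does not change the power at the 0.5 on which 4.4 is built.
- **Baseline handling is SAP detail.** A model with baseline means constrained equal would earn about the full gain, and 1 – r² suggests that adjustment was intended. So this is an open choice rather than a proven loss. But the protocol does describe the model, with baseline as an outcome row and covariates chosen by observed imbalance, and that description does not secure a gain already spent in 4.4.

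**Conclusion.** The point holds and should be fixed. At the protocol's own inputs, the stated 80% is not the power of the model in section 8.

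If all 40% is lost by T1, with 9 groups and the baseline gain earned, a true 0.5 SD effect is missed about 22–28% of the time (residual df) or 24–31% (Satterthwaite), rather than 20%, for an assumed ICC of 0.02–0.10. If only 20% is lost by T1, power is 81–88% or 78–86% respectively, and the claim largely stands.

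The unsecured baseline adjustment could cost a further 6–8 points, whichever of these two losses applies. Both parts concern power only.

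**What to change.** **Section 8.1.** State that the primary test is the MBCT + TAU versus TAU contrast in IDS-C at T1. Take it from the repeated-measures model with T1–T5 as outcome rows and baseline IDS-C as a fixed covariate (or baseline kept as a row with one mean common to both arms). Include a random therapy-group effect in the MBCT arm only and a small-sample df method such as Satterthwaite.

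**Section 4.4.** Keep N = 160 and restate power for that model, with the ICC range and T1 loss labelled as assumptions. Suggested content, using Satterthwaite df to match 8.1: with about 9 MBCT groups and ICC 0.02/0.05/0.10, power is about 76/73/69% if 40% is lost by T1 and 86/83/78% if 20% is lost; 80% is kept while T1 loss stays below about 33/27/13%.

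**Cost.** Wording in two sections, with no extra patients, visits or data. The quoted power at 40% loss drops below 80%, and at that loss the treatment test has about 21–26 degrees of freedom with 9 groups instead of 94.
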